STUDY PROTOCOL AND STATISTICAL ANALYSIS PLAN

Official title: Furoscix in Heart Failure Patients with Diuretic Resistance

NCT number: NCT05528588

IRB Approved date: 07-22-24

Form A

IRB #

STU-2022-0768

PROTOCOL FORM / RESEARCH DESCRIPTION

If an item does not apply to your research project, indicate that the question is "**not applicable**" – do not leave sections blank

Click once on the highlighted entry in each box to provide your response. Click the item number/letter or word, if hyperlinked, for detailed instructions for that question. If your response requires inserting a table, picture, etc, you may need to first delete the box that surrounds the answer and then insert your table or other special document.

1. Purpose and objectives. *List the purpose and objectives:*

The purpose of this study is to assess the diuretic efficiency of subcutaneous furosemide (Furoscix) compared to oral diuretic therapy for patients post heart failure (HF) hospitalization and evaluate the impact of diuretic resistance as identified by the BAN-ADHF (Blood urea nitrogen, creatinine, Natriuretic Peptide levels, Atrial fibrillation, Diastolic blood pressure, Hypertension and Home diuretic dose, and Heart Failure hospitalization) risk score.

Key Outcomes:

1. Post-treatment urine output over 8 hours. This will be assessed in mL per mg of treatment (Furoscix vs. oral diuretic).
2. Post-treatment urine sodium. Urine sodium will be assessed hourly over 8 hours post-treatment.

Safety Outcome Measures:

1. Number of participants with post-intervention need for emergency department visit or hospitalization. The count of participants with post-intervention need for emergency department visit or hospitalization for worsening heart failure is assessed.

Goals: Successful completion of this project will establish proof of concept that Furoscix provides more effective post-hospitalization diuresis than the traditional oral dose in a diuretic resistance patient population. This study will provide pilot data to guide the design of larger studies involving a diuretic-resistant heart failure population.

2. Background.

- Describe past experimental and/or clinical findings leading to the formulation of your study.
- For research involving investigational drugs, describe the previously conducted animal and human studies.
- For research that involves FDA approved drugs or devices, describe the FDA approved uses of this drug/device in relation to your protocol.
- Attach a copy of the approved labeling as a product package insert or from the Physician's Desk Reference.

You may reference sponsor's full protocol or grant application (section number and/or title) or if none, ensure background includes references.

Please respond to all components of this item, or clearly indicate which components are not applicable.

a. Background

Form A

IRB #

STU-2022-0768

Introduction

Heart failure is one of the leading causes of hospitalization in the United States, contributing to over 1 million emergency department visits and nearly 1 million hospitalizations for HF annually.¹ The estimated mean cost for HF was \$11,552 in 2014, totaling an estimated \$11 billion.² Thus, strategies to reduce the burden of acute care use for patients with heart failure are necessary. Acute decompensation of heart failure is characterized by volume overload and is primarily treated with intravenous diuretics. However, inefficient and ineffective diuresis both during hospitalization and in the post-discharge environment predispose patients to frequent readmission and a worse prognosis.³ Importantly, there is heterogeneity in patient response to intravenous diuresis, with an estimated 20-50% of patients having poor response to initial IV diuretic therapy.³ Patients who are resistant to intravenous diuresis have increased risk of re-hospitalization and mortality. Importantly, our group recently derived an integer-based risk score (BAN-ADHF score) to predict patients with low diuretic efficiency, with the research winning the NHLBI Heart Failure Data Challenge.^{4,5}

As part of patient's standard of care, they receive oral diuretics, including furosemide or torsemide, which are FDA approved for treating congestion and volume overload from heart failure. However, some patients are "resistant" to oral diuretics and have higher risk of repeat hospitalization. Therefore, purpose of this study is to evaluate treatment with subcutaneous furosemide (Furoscix) compared with oral diuretic therapy for patients with recent heart failure hospitalization either with or without diuretic resistance.

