Intervention, Setting, and Design: We are recruiting patients from UTSW and Parkland. All of the research procedures in this study will take place at the Clinical Research Unit in the Aston Building at UT Southwestern Medical Center. This will be a randomized, open-label pilot study of 70 patients with and without diuretic resistance who were recently admitted and discharged for acute decompensated heart failure with an oral diuretic regimen testing whether Furoscix is more effective at achieving post-discharge outpatient diuresis than oral diuretics. Diuretic resistance will be identified using the BAN-ADHF (Blood urea nitrogen, creatinine, Natriuretic Peptide levels, Atrial fibrillation, Diastolic blood pressure, Hypertension and Home diuretic dose, and Heart Failure hospitalization) score which has been integrated into the electronic health record. The score is integer-based with a score of ≥ 12 indicating diuretic resistance with high likelihood of poor outcomes.

Screening:

- We are requesting a partial HIPAA waiver to review electronic health records and confirm their eligibility in the study. Pre-screening will occur through the electronic health record to evaluate for inclusion and exclusion criteria and to assess if women of child-bearing potential have a pregnancy test to confirm they are not pregnant. Lab testing will be reviewed. These include review of urine drug screen, alcohol screen (if clinically indicated), NT-proBNP, creatinine clearance.
- BAN-ADHF score will be calculated.

Form A

IRB #

STU-2022-0768

- After patients are screened, patients will be approached for potential participation. If patients are interested, they will be scheduled for an in-person randomization visit optimally within 1-7 days of hospital discharge, although patients will be eligible up to 14 days after discharge.
- At the research appointment, patients will be asked if they are interested in voluntarily participating in this study.

Research Visit:

Pre-Randomization:

- Confirm eligibility
- Obtain informed consent
- Physical exam including vital signs assessment.
- Prior and concomitant medication assessment.

Randomization:

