- Collect approximately 10 mL of blood for a blood test to check patient's electrolytes. This will be done at the end of the research visit.
- Call participants in 7 days after their research visit to assess if patient has had a presentation to urgent care, emergency department, or is re-hospitalized for acute exacerbation in heart failure.

Compensation:

To account for a full day of research monitoring, patients will be compensated \$250 for their participation in the study with the UTSW ClinCard.

Data Safety and Monitoring:

Patient safety will be tracked over the study. For any adverse events (AE) that occur during their participation in the study, medical care will be provided and patients will be followed until resolution. See Form D for more details.

Form A

IRB #

STU-2022-0768

Privacy and Confidentiality:

To protect patient's privacy and confidentiality, we will ensure the consent process takes place in a private area and conduct research in secure areas where others will not have access to their PHI. All PHI collected during the study will be coded with a Subject ID using a randomized code. The key to the code will be kept on a password database in the research coordinator's locked office. Only authorized personnel listed on Form B will have access to the data. Any hard copy documents such as the signed consent form will be kept in the research coordinator's locked office.

Statistical Analysis:

This study will assess the primary outcomes of greater diuretic efficiency as measured by total urine output and urine sodium. As the Furoscix group will receive 80 mg of subcutaneous furosemide and the control group will take a home dose of oral diuretic, urine output will be normalized per mg of treatment administered. Differences in total urine produced will be compared between Furoscix versus oral diuretic groups. The urine sodium will be assessed hourly, and will be compared across the two groups.

As this study is a preliminary pilot study to assess the effect of Furoscix on diuretic efficacy, we have chosen a convenience sample of 70 patients to allow for a comparison between patients who receive Furoscix and those who do not receive Furoscix. The results of this trial will serve as a precursor for a larger, multicenter trial of Furoscix in patients with diuretic resistance.

4.b. List of the study intervention(s) being tested or evaluated under this protocol

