	
 individual procedures 
example: Eligibility Assessments 
 History and physical Questionnaire Laboratory tests 
 
Add or delete rows as needed
	Local Standard Practice Indicate the number of times each procedure will be performed as stipulated in the research plan that would be performed if the participant were not participating in the study.	Research Only Indicate the number of times each procedure will be performed solely for research purposes (meaning that the participant would not undergo the same number of procedures or would not undergo the procedure(s) at the same frequency if they were not participating in the study)	Risks If you are requesting a Waiver of Informed Consent, complete the table below. List the reasonably expected risks for each procedure or group of procedures under the following categories as appropriate: 
 • Serious and likely; • Serious and less likely; • Serious and rare; • Not serious and likely; • Not serious and less likely
1	Screening for Eligibility in Medical Records	N/A	Multiple Times	Breach of confidentiality; not serious and less likely
	Insert procedure here			
	Insert procedure here			
	Insert procedure here			
2	CRU visit			
	Screening Procedures	N/A	Once	N/A-See risks in the consent form
	Urine samples	N/A	Multiple times	N/A-See risks in the consent form
	10 mL blood draw		Once	N/A-See risks in the consent form
3	Post-CRU visit follow-up			
	Call patient to assess whether they were hospitalized in 7 days post discharge	N/A	Once	N/A-See risks in the consent form
	Insert procedure here			
	Insert procedure here			
4	Insert component 4 here			
	Insert procedure here			
	Insert procedure here			
	Insert procedure here			

5. Safety Precautions. (Describe safeguards to address the serious risks listed above.)

a. Describe the procedures for protecting against or minimizing any potential risks for each of the more than minimal risk research procedures listed above.

Risks and side effects related to Furoscix include those which are:

Likely, some may be Serious

In 100 people, approximately 21-100 may have:

- Dehydration
- Electrolyte depletion, including low potassium (hypokalemia), low sodium (hyponatremia), low magnesium (hypomagnesemia), low calcium (hypocalcemia).
- Dry mouth
- Thirst

Form A

IRB #

STU-2022-0768

- Weakness
- Muscle pains or cramps
- Low blood pressure
- High heart rate

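### The only named safety outcome is defined by worsening heart failure, so acute-care visits for the other listed drug risks do not count, and no by-arm safety summary is stated

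*Combined protocol and SAP*

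**What the plan says.** Section 1 (Safety Outcome Measures) has a single item. Its label carries no cause: "Number of participants with post-intervention need for emergency department visit or hospitalization". The sentence that defines it does: "The count of participants with post-intervention need for emergency department visit or hospitalization for worsening heart failure is assessed".

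Section 4.a (Other research procedures) describes how the events are found: "Call participants in 7 days after their research visit to assess if patient has had a presentation to urgent care, emergency department, or is re-hospitalized". That sentence closes by naming acute exacerbation of heart failure. Table 4.d describes the same call as asking about hospitalization only, without a cause, and counts the 7 days from discharge.

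Section 5.a lists, under the band "In 100 people, approximately 21-100 may have", dehydration, electrolyte depletion, low blood pressure and high heart rate for both treatments, and arrhythmia for Furoscix only. Deterioration in kidney function is in the next band for both.

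Blood for electrolytes is drawn once: "This will be done at the end of the research visit". Adverse events are to be tracked, treated and followed (4.a, Data Safety and Monitoring; 5.b), with further detail left to Form D, which is not among the documents. The Statistical Analysis section covers urine output and urine sodium and does not mention safety.

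**The concern.** A safety outcome for a diuretic comparison should be able to register harm from too much diuresis as well as from too little. As defined, this one registers only the second. A participant who goes to the emergency department with hypotension or hypokalaemia in the week after dosing is not a case, because the visit is not for worsening heart failure.

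The protocol's own rationale makes this matter. Section 2 says that "inefficient and ineffective diuresis both during hospitalization and in the post-discharge environment predispose patients to frequent readmission and a worse prognosis", and the trial is described as "testing whether Furoscix is more effective at achieving post-discharge outpatient diuresis than oral diuretics". On that reasoning, a treatment that succeeds on diuresis should, if anything, lower the count. The pilot is meant to inform a larger trial. It would serve that purpose poorly if its one safety count were silent on the harms that its own risk section names.

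**Working it through.** There is no figure in the plan to reproduce: 70 is a convenience sample, and no event rate, alpha or power is given. The check is therefore mainly a comparison of texts, followed by an illustration.

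**1. The descriptions of the outcome, side by side**

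| Place | Events | Cause | Window |
|---|---|---|---|
| Section 1, label | ED, hospital | none stated | none stated |
| Section 1, definition | ED, hospital | worsening heart failure | none stated |
| 4.a, telephone call | urgent care, ED, hospital | heart failure exacerbation, at the end of the sentence | 7 days after the research visit |
| 4.d, entry for the call | hospital only | none stated | 7 days after discharge |

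They differ on events, cause and starting point.

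**2. What the starting point does.** Section 4.a allows the visit up to 14 days after discharge and prefers days 1 to 7. If the visit is on day v, a window of 7 days from discharge leaves max(0, 7 − v) days after treatment:
- v = 1: 6 days
- v = 4: 3 days
- v = 7 or later: 0 days

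The window in 4.a always gives 7.

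**3. How the cause restriction can change the reading.** The rates below are assumptions, because the documents give none. Let h be the probability of a heart failure presentation and o that of a presentation for over-diuresis (volume, blood pressure, electrolyte or renal). Taking the two as independent, any-cause = 1 − (1 − h)(1 − o). Differences are Furoscix minus control.

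- **Scenario A:** h 15% control, 7.5% Furoscix; o 2% and 10%. Heart failure only: −7.5 points. Any cause: (1 − 0.925 × 0.90) − (1 − 0.85 × 0.98) = 0.1675 − 0.1670 = +0.05 points, in effect zero.
- **Scenario B:** h 10% and 5%; o 2% and 10%. Heart failure only: −5 points. Any cause: (1 − 0.95 × 0.90) − (1 − 0.90 × 0.98) = 0.145 − 0.118 = +2.7 points.
- **Scenario C:** h 10% and 5%; o 2% in both arms. Heart failure only: −5 points. Any cause: (1 − 0.95 × 0.98) − 0.118 = 0.069 − 0.118 = −4.9 points.

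So the restriction is nearly harmless if over-diuresis visits do not differ by arm. It can reverse the reading if they do.

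**4. What 35 per arm can show** (70/2 under 1:1 allocation; two-sided alpha 0.05 assumed)
- At an assumed 7-day heart failure rate of 5% to 20%, the control arm expects 35 × 0.05 = 1.75 to 35 × 0.20 = 7 events. Power to detect a halving is 0.08 to 0.21.
- In Scenario B, the standard error of the any-cause difference is √[(0.118 × 0.882 + 0.145 × 0.855)/35] = √(0.2281/35) = 0.0807. The expected 95% interval is 2.7 ± 1.96 × 8.07 = 2.7 ± 15.8, or −13.1 to +18.5 points.
- If an arm has no event, the one-sided 95% upper bound is 1 − 0.05^(1/35) = 8.2%.

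Any of these summaries would be descriptive.

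**The case against.** The strongest reply is that safety data are not missing. A research nurse monitors each participant, adverse events are documented and followed, and electrolytes are drawn after dosing. A reader might infer that over-diuresis harms cannot be seen in this trial at all. The documents do not support that: the harms can be recorded, and Form D, which is not available, may say more about adverse events. What stands against the plan is narrower. The named outcome excludes these harms, and these documents state no by-arm summary.

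Secondly, the cause restriction is not uniform. The label and table 4.d omit it, and in 4.a the closing phrase may qualify only re-hospitalization. That is a fair reading, but the explicit definition in section 1 is restrictive, so the ambiguity needs resolving. An any-cause reading would in any case still miss harms that do not lead to acute care.

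Thirdly, the direction is inferred. No estimate shows that one administration changes heart failure visits within 7 days, and with no safety comparison stated, the plan does not itself conclude that Furoscix is safer. Both points stand. The exclusion of other causes does not depend on either.

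Fourthly, a reader might want to reclassify the heart failure count as efficacy. The documents do not require that. Participants are told not to take their home dose before the visit, and the Furoscix arm receives a substitute for it, so worsening heart failure afterwards is a legitimate harm to count.

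**Conclusion.** The point holds in limited form and should be acted on. Read literally, the single safety outcome omits acute-care visits for risks that section 5.a itself lists. Four descriptions of the outcome disagree, and the statistical section gives no by-arm safety summary. The primary comparisons of urine output and sodium are unaffected.

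The size cannot be derived from the documents. Under assumed rates, the gap between the defined count and an any-cause count runs from about 0.1 point (Scenario C) to about 7.5 to 8 points (Scenarios B and A). These figures rest on independence of the two kinds of visit and on rates chosen for illustration.

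A reader might multiply the 21 per 100 in section 5.a by 35 and conclude that about 7 participants per arm will have each likely harm. That is not supported. The figure is the edge of a broad risk band rather than an incidence. The band is the same in both arms for most of these harms, and arrhythmia is not on the oral list. Section 5.a also anticipates few side effects, because participants already take diuretics.

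**What to change.** 1. Reconcile section 1, the call in 4.a and the entry in 4.d on events, cause and starting point.
2. Define the safety outcome as the number of participants with any urgent care, emergency department or hospital presentation, for any cause, in the 7 days after the research visit. Record the cause (worsening heart failure; volume depletion or hypotension; electrolyte; renal; other) and tabulate by arm. Because the trial is open-label, an any-cause count also depends less on judgement about the reason for a visit.
3. Keep the worsening heart failure count beside it as a safety component.
4. Add to the Statistical Analysis section a descriptive by-arm report of end-of-visit electrolytes and recorded adverse events, with estimates and 95% confidence intervals and no formal test. No electrolyte draw before dosing at the visit is described, so compare post-dose values between randomized arms rather than change from baseline.

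Do not promise tables of post-dose blood pressure or renal function: vital signs are described only before randomization, and the blood test is described as electrolytes only. Such events would enter only as recorded adverse events or causes of presentation.

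The cost is rewording, one added question in a call already planned, and tabulation of data already collected. The downside is that the any-cause count will include some unrelated visits, which dilutes it; the cause table limits that.

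### The only named safety outcome leaves out death, and the day-7 call records no vital status, so a death without a heart failure visit adds nothing to the safety count

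*Combined protocol and SAP*

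**What the plan says.** Section 1 (Safety Outcome Measures) lists a single item. Its explanatory sentence reads: "The count of participants with post-intervention need for emergency department visit or hospitalization for worsening heart failure is assessed". It mentions neither death nor a time window.

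Section 4.a (Other research procedures) gives the only stated way of collecting this outcome. It is a telephone call to the participant 7 days after the research visit, "to assess if patient has had a presentation to urgent care, emergency department, or is re-hospitalized for acute exacerbation in heart failure". The procedures table in section 4.d describes the call more narrowly and with a different starting point: "Call patient to assess whether they were hospitalized in 7 days post discharge".

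Mortality enters the text as a reason for the research. The background in section 2.a states: "Patients who are resistant to intravenous diuresis have increased risk of re-hospitalization and mortality". Apart from that sentence it appears only in the title of a cited reference.

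Separately, section 4.a (Data Safety and Monitoring) provides for adverse events: "For any adverse events (AE) that occur during their participation in the study, medical care will be provided". Follow-up runs until resolution, and the reader is sent to Form D for detail. Section 5.b repeats this and adds that events will be documented.

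**The concern.** A safety outcome should not record the worst result as no event. Here, a participant who goes home after the visit and dies without first attending an emergency department or being admitted for worsening heart failure does not meet the definition. That participant also cannot answer the call. The documents name no second source, such as a relative or the health record, and give no rule for participants who are not reached.

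What is at stake is how the one named safety result is read. The section 1 goals and the closing paragraph of the Statistical Analysis text both present the trial as the basis for larger studies in diuretic-resistant patients, a group the background says has raised mortality. With a handful of events at most, a single patient on the wrong side of the definition would be visible in an arm's figure. The same definition might also be carried into the next trial.

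**Working it through.** **Figure to reproduce.** There is none. The plan states no event rate, mortality, power or error rate, and says "we have chosen a convenience sample of 70 patients".

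**Reading the definition against its source.**

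| Place | What it captures | Death or vital status? |
|---|---|---|
| Section 1, safety outcome | ED visit or hospitalization for worsening heart failure | No |
| Section 4.a, day-7 call | Urgent care, ED or re-hospitalization for heart failure exacerbation, after the visit | No |
| Table 4.d, call | Hospitalization, with the 7 days counted from discharge | No |
| Sections 4.a and 5.b, adverse events | Any adverse event, with detail in Form D | Possibly; Form D not supplied |

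The instruction above table 4.d says that tables 4.b and 4.d together should cover all research procedures. Neither has a vital-status item. It follows directly that a death without a qualifying visit contributes 0 to the count. Whether that participant would be reported as event-free, as missing or as a death is not stated.

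**Size.** Inputs from the documents: n = 70, randomised 1:1 within score strata, so about 70/2 = 35 per arm. Input assumed: the 7-day risk of death, m, from 0.25% to 2%.

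Expected deaths = 70 × m. Chance of at least one = 1 − (1 − m)^70.

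| Assumed m | Expected deaths in 70 | Chance of at least one |
|---|---|---|
| 0.25% | 0.18 | 16% |
| 0.5% | 0.35 | 30% |
| 1% | 0.70 | 50% |
| 2% | 1.40 | 76% |

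These figures are for death from any cause. The gap concerns only deaths with no earlier heart failure ED visit or admission, so each percentage is an upper limit for the chance that the count misses a death.

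**Effect of one patient on an arm.** 1/35 = 2.9 percentage points. With exact (Clopper-Pearson) 95% limits, 0/35 gives 0 to 10.0%, and 1/35 gives 0.1 to 14.9%. The point estimate changes from none to one, while the two intervals overlap almost entirely.

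**The case against.** Several stronger readings are tempting, and the documents do not support them.

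- **Deaths would go unrecorded.** A reader might infer this, but adverse events are to be tracked, documented and followed, with detail in Form D. That form was not supplied, so the inference cannot be made. What remains is narrower: an adverse event record does not put the death into the named outcome or say how the participant is counted there.
- **One omitted death could reverse the safety comparison.** The Statistical Analysis text compares the groups on urine output and urine sodium only. The safety outcome is a count with no test, estimate or decision rule attached. So few events could not support a comparison between arms even with death included.
- **A participant who dies is scored as event-free.** This is one possible outcome of a missing rule. A death learned of at the call could equally be reported as a death.
- **A missed death is likely.** The mortality range is assumed and the probabilities are upper limits. The true risk may be below the range: section 4.a excludes, among others, patients with a recent ICU stay, inotrope use, low-output heart failure or systolic pressure below 100, and participants must attend a day-long outpatient visit. The background sentence on mortality gives no time frame and concerns resistant patients, whereas the trial also enrols patients without resistance. At an assumed 0.1%, the chance of any death is 1 − 0.999^70, about 7%.

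These points limit how much the gap matters. They do not close it, because the definition omits death and no text supplies a counting rule.

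**Conclusion.** The point holds as a gap in the outcome definition. The one named safety outcome excludes death, its listed source does not ask about vital status, and a death without a qualifying heart failure visit adds nothing to the count. That much rests on the text alone.

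The size rests on an assumed 7-day mortality of 0.25% to 2%, which gives at most a 16% to 76% chance that the situation arises among 70 patients, and on roughly equal arms. Materiality is modest for a pilot with one day of study treatment and a single call a week later. The change is still worth making, because it is cheap and the present definition gives no weight to the most serious event that could occur in follow-up.

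**What to change.** Define the safety outcome as the number of participants who die from any cause, or have an ED visit or hospitalization for worsening heart failure, within 7 days of the research visit. Report it by arm, with the heart failure component and all-cause deaths as separate lines, so that the existing outcome stays visible. Keep the heart failure restriction; whether to count visits for other causes is a separate question.

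Record day-7 vital status for every randomised participant, using the health record for those the call does not reach, and state how participants with no information are counted. Bring table 4.d into line with section 4.a on the starting point of the 7 days. The visit can take place up to 14 days after discharge, so a week counted from discharge could end before the visit.

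The cost is a small amendment to a stated outcome in an IRB-approved protocol, one extra field on the follow-up form, and a count that may look slightly less favourable. The sample size does not change.
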